Merck Investigator Studies Program (MISP)

IIS Protocol Template

Requirements for Submitting a Full Proposal

[figure not shown]
Section #1 - MISP Protocol Identification

Study Title:	A double-blind, randomized and controlled multicenter prospective trial to compare the oncological benefit of deep neuromuscular block in gastric cancer obesity patient
Request Date:	3rd August 2016
Last update date:	8th May 2020
Institution Name	Korea University College of Medicine
Investigator Contact Information: - Full address - Phone No. - Fax No. - E-mail	[name] Addr, Department of Surgery, [name] Tel, [name] Fax, [name] Email, [contact]

Registered in www.clinicaltrials.gov as NCT03196791

Section #2- Core Protocol	
2.1 Objectives & Hypotheses	
2.1 List the objectives.
 
The present randomized study is designed to evaluate the impact of muscle relaxation during laparoscopic gastrectomy on oncological benefit, especially with obese patients over BMI 25. Because surgeons still find that laparoscopic surgery for obese patients is challenging. The retrieval of lymph nodes (LNs) is difficult because they are embedded in thick fat tissue and are hard to distinguish with surrounding fat so that, the operative time should be prolonged. Studies have revealed that the association between obesity and longer operative outcomes than normal body weight patients. Therefore we assumed deep neuromuscular block was associated more adequate lymphadenectomy, smaller intraoperative bleeding, shorter operative time.
 
2.1.1 List the clinical hypotheses.
 
The primary endpoint is number of harvested lymph node that is critical point regarding quality of surgery in gastric cancer treatment. The secondary endpoint is intraoperative bleeding, surgeons' satisfaction.

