-----------------------------	--

	
If TOF count 1-2, rocuronium bromide 0.1-0.5 mg/kg/hr continuous infusion with TOF monitoring
 
In Deep neuromuscular group followed by a continuous infusion of 0.5–1.0 mg/kg/hr (IBW) with TOF monitoring
 
10. Additionally, if the surgeon asked the anesthesiologist for deeper NMB to achieve an adequate surgical field, rocuronium bolus 0.15 mg/kg was administered.
 
11. rocuronium infusion stop at end of Laparoscope
 
12. Reversal agent & Dose protocol
 
 -In Moderate neuromuscular group (second twitch appeared at TOF) Sugammadex 2mg/kg (Bridion®, (MSD)) -In Deep neuromuscular group (end of surgery) Sugammadex (Bridion®, Merck Sharp and Dohme (MSD), Oss, The Netherlands) 4 mg/kg 
13. When the TOF ratio recovered to 0.9 and spontaneous breath, opening of the eyes to verbal commands, extubation will be done.
 
14. Insufflation pressure: 12mmHg
 
Evaluation method
 
At OR : Anesthesiologists
 
 Total anesthesia time Total surgical time (Incision – dressing) The time from the end of the operation to the administration of the reversal agent Total fluid Total rocuronium dose Hemodynamic parameter systolic,diastolic,mean BP -HR -EtCO₂ -Temperature -Peak inspiration pressure 
Sedation score(MOAA/S)
 
  
 0	does not respond to pain	
 
 1	does not respond to mild prodding or shaking	
 
 2	responds only after mild prodding or shaking	
 
 3	responds only after name is called loudly and/or repeatedly	
 
 4	lethargic response to name spoken in normal tone	
 
 5	responds readily to name spoken in normal tone	
  
 
Surgeon
 
Report of surgeon's specific complaints
 
The wasting operative time due to poor neuromuscular relaxation
 
Patient motion
 
Surgical rating score : consists of individual 4 parts of critical lymph node dissection areas -
 
during lymph node dissection at 4sb, 6, supraduodenal area and suprapancreatic area
	0	does not respond to pain	1	does not respond to mild prodding or shaking	2	responds only after mild prodding or shaking	3	responds only after name is called loudly and/or repeatedly	4	lethargic response to name spoken in normal tone	5	responds readily to name spoken in normal tone

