2.7 Statistical Analysis and Sample Size Justification	
Statistical analyses were performed with IBM SPSS 20 software. Quantitative variables were expressed as means (standard deviation) and were compared by Mann-Whitney and Wilcoxon nonparametric tests. Qualitative variables were described by numbers and percentages and 95% confidence intervals. The various parameters were compared by Pearson' s and Fisher's Chi-squared tests. For all statistical tests, a P value < 0.05 was considered significant
 
The major objective of this study is to estimate the number dissected lymph nodes. Based upon a sample size of n=89 patients per group, this study has 80% power to detect a 6.3 difference between groups in harvested lymph nodes; this calculation is based on a between subject standard deviation of change of 15 for harvested lymph node (reference for where this variability statement originated). The calculations are the customary ones based on normal distributions –estimation of sample size and power for comparing two means in Bernard Rosner's fundamentals of biostatistics. After considering 10% of follow-up loss, a total of 196 patients will be needed.
 
Regarding increasing effect of BMI on surgery, we will process it as continuous variable when we analyze data and if there is significance, we could decide a cut off value of BMI for specific anesthetic indication.
 
In addition, to control the surgeons' factors impacting results, we will perform surgeon stratified randomization. And if there is a serious surgeon's technical problems being able to distort objective data when interim analysis, we would drop the surgeon out of this study.

2.8 Specific Drug Supply Requirements	
N/A

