2.12 Publication Plan	
Expected number of papers published with this trial: 1 paper –to make a high impact result, we are going to incorporate all surgical and anesthetic variables altogether. But if we could make collateral data, there would be more.
 
Target journal: Annals of Surgery
 
Abstracts: 2 to 3

	Scientific meetings considered with this study results: SAGES and ACS, and Korean International Surgical Meetings including KINGCA and KSELS.
2.13 Curriculum Vitae	Annexed sheet
2.13 Protocol Submission for Investigator-Initiated Studies	
U.S. protocols should be submitted by US investigators directly or through the Global Research Specialist at www.merckiiisp.com
 
Non U.S. protocols should be submitted to the MSD office by the investigators.

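### Section 2.7 calls every P<0.05 significant, and none of the roughly 15 to 27 outcomes beyond the primary has multiplicity control or an exploratory label

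*Combined protocol and SAP*

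**What the plan says.** Section 2.7 of the combined protocol and SAP sets a single threshold: "For all statistical tests, a P value < 0.05 was considered significant". It gives no multiplicity adjustment and no order of testing, and it labels no analysis as exploratory.

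Section 2.1.1 does set a partial hierarchy. For the primary it says: "The primary endpoint is number of harvested lymph node that is critical point regarding quality of surgery in gastric cancer treatment". It then continues "The secondary endpoint is intraoperative bleeding", with surgeons' satisfaction as the other secondary and no order between the two. Satisfaction is not defined as a variable; the nearest instrument is the 1-to-5 surgical rating in section 2.5, scored in four dissection areas.

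Section 2.5 lists the other measures under its evaluation method. They are operating-room measures (including "Hemodynamic parameter systolic,diastolic,mean BP"), surgeon reports and ward outcomes, with no ranking.

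Section 2.12 expects one paper: "to make a high impact result, we are going to incorporate all surgical and anesthetic variables altogether".

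Section 2.7 also lets a significant BMI finding lead to a BMI cut-off for an anaesthetic indication.

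**The concern.** Where many outcomes share one unadjusted threshold, some will cross it by chance. Under the rule as written, a nominal P<0.05 on first flatus, rescue medication or peak airway pressure has the same standing as one on bleeding. If the node count showed no difference, nothing in the plan would stop a chance finding elsewhere from being declared significant and becoming the main message. The two named secondaries are not protected either: each is tested at 0.05 with no joint control. The same threshold governs the BMI analysis, which is not in the counts below.

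**Working it through.** **1. The plan's own figure.** Inputs from section 2.7: "Based upon a sample size of n=89 patients per group, this study has 80% power to detect a 6.3 difference between groups", with a "between subject standard deviation of change of 15 for harvested lymph node".

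n per group = 2 × [15 × (1.960 + 0.842) / 6.3]² = 88.99, so 89. Power at 89 per group is 80.0% by the normal formula. The plan does not state sidedness. A one-sided 0.05 would need only 71, so two-sided 0.05 is what was used, and it was spent on one endpoint. For loss, the plan says "After considering 10% of follow-up loss, a total of 196 patients will be needed": 178 × 1.10 = 195.8, so 196. (Dividing by 0.9 would give 198, a small difference that does not bear on this point.) The documents state no family-wise error rate to reproduce.

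**2. Outcomes beyond the primary** (sections 2.1.1 and 2.5).
- Operating room, 13: anaesthesia time, surgical time, time to reversal, fluid, rocuronium dose, systolic, diastolic and mean BP, heart rate, EtCO₂, temperature, peak inspiratory pressure, sedation score.
- Surgeon, 4: complaints, wasted operative time, patient motion, rating score.
- Ward, 5: VAS pain, PONV, rescue medication count, first flatus, complications to day 30.
- Bleeding, 1.

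The total is 13 + 4 + 5 + 1 = 23, with satisfaction read as the rating score.
- Low count: treat the seven haemodynamic and ventilation items as one (−6) and the three surgeon reports as one (−2), giving 15.
- High count: test the rating in each of its four areas (+3) and count satisfaction separately (+1), giving 27.
- Rocuronium dose differs by design and the reversal triggers differ by arm, so neither is a natural null. Removing both from 23 leaves 21, so about 20 is a fair working figure.

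**3. Chance of at least one false positive, independent tests, all nulls true:** 1 − 0.95^m.

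| m | chance |
|---|---|
| 2 (named secondaries) | 9.8% |
| 13 | 48.7% |
| 14 | 51.2% |
| 15 | 53.7% |
| 20 | 64.2% |
| 23 | 69.3% |
| 27 | 75.0% |

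With 20 true nulls the expected number of false positives is 20 × 0.05 = 1.0, whatever the correlation.

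**4. Effect of correlation.** The documents give none, so these are assumptions. Simulated two-sided z-tests with one common correlation, 200,000 runs each, m = 20:

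| correlation | chance |
|---|---|
| 0.1 | 62.5% |
| 0.2 | 58.9% |
| 0.3 | 53.9% |
| 0.5 | 41.9% |
| 0.7 | 28.9% |

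An assumed block pattern over 22 outcomes (correlation 0 to 0.8 within blocks, none between) gives 62.3%.

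**5. Effect of control.** Testing the two secondaries at 0.05 / 2 = 0.025 each holds their joint error at or below 5% (1 − 0.975² = 4.9% if independent). Holm does at least as well. Testing them only after a significant primary keeps the error over all three endpoints at or below 5%.

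**The case against.** There is a fair case that this is a modest, familiar gap.

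- **The primary is sound.** There is one primary endpoint, sized for its own two-sided 0.05. This stands: nothing here weakens the node-count test.
- **Many listed items are monitoring data.** Section 2.5 manages BP and EtCO₂ to targets, and a temperature difference is unlikely to become a headline. Three BP values, heart rate, EtCO₂, temperature, peak pressure, fluid and sedation score make nine. Without them, and without rocuronium dose and time to reversal, 23 − 9 − 2 = 12 outcomes remain, and 1 − 0.95^12 = 46.0%. This lowers the figure, but the rule covers all tests and exempts none of these.
- **Not every null need be true.** Section 2.1 hypothesises less bleeding and shorter operative time. This also stands as a limit on the calculation.
- **Secondary outcomes often go unadjusted.** That is defensible when they are labelled exploratory. Here they are not.

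A reader might also infer four stronger things that the documents do not support:

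1. That a false claim is more likely than not. This needs at least 14 independent true nulls, and with 20 tests it fails by a common correlation of 0.5.
2. That all of the roughly 20 outcomes are unranked. Bleeding and satisfaction are named secondaries; they lack an order and error control, not a rank.
3. That haemodynamics are tested at many time points. Section 2.5 gives no schedule for them; only VAS, collected to 48 hours, implies repetition.
4. That section 2.12 plans to let any positive result carry the paper. The sentence explains why one combined paper is expected. It sets no rule for claims, and reporting everything together also guards against selective reporting.

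**Conclusion.** The concern holds in a limited form. No outcome beyond the primary has multiplicity control or an exploratory label, while section 2.7 allows any of them to be called significant at P<0.05. With about 20 independent true nulls, the chance of at least one false positive is about 64%, falling to 54% and 42% at common correlations of 0.3 and 0.5. Even at 0.7 it is 28.9%, nearly six times the nominal 5%. For the two named secondaries alone it is 9.8% if independent.

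These figures rest on an outcome count that can be read as anything from 15 to 27, on all nulls being true, and on assumed correlations. They show the scale of the exposure and do not predict this trial's result. The change should be made because it costs little; the primary analysis does not depend on it.

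**What to change.** Replace the single rule in section 2.7 with three statements.

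1. Only the harvested node count is confirmatory, at two-sided 0.05.
2. The two named secondaries are tested under a pre-specified multiplicity rule, for example Holm after a significant primary. A fixed order would also serve. Surgeons' satisfaction must first be defined, as one per-patient summary (such as the mean) of the four-area surgical rating score; otherwise the test cannot be run as specified.
3. Every other variable, including operative time, is labelled exploratory and reported as a between-arm estimate with a 95% confidence interval, without the word significant. VAS, and any haemodynamic variable that is recorded repeatedly, is reduced to one pre-specified summary per patient.

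The single combined paper in section 2.12 can stay. The change needs wording only: no extra patients and no new data. The downside is that fewer outcomes can be called significant. Operative time in particular becomes descriptive although section 2.1 hypothesises a benefit, so the investigators should accept that knowingly.

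### The stated 80% power is for a comparison of two means; the rank test the plan names has about 77% after the full 10% loss, on the plan's own normal assumption

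*Combined protocol and SAP*

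**What the plan says.** Section 2.1.1 sets the outcome: "The primary endpoint is number of harvested lymph node". Section 2.7 says that quantitative variables "were compared by Mann-Whitney and Wilcoxon nonparametric tests". For qualitative variables it names Pearson and Fisher tests. It names no t-test, linear model or other comparison of means, and gives the primary endpoint no test of its own.

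The sample size statement, also in section 2.7, reads: "Based upon a sample size of n=89 patients per group, this study has 80% power to detect a 6.3 difference between groups". It assumes an SD of 15 and describes its method in two phrases: "The calculations are the customary ones based on normal distributions" and "estimation of sample size and power for comparing two means". The loss allowance follows: "After considering 10% of follow-up loss, a total of 196 patients will be needed". On significance: "For all statistical tests, a P value < 0.05 was considered significant". Sidedness is not stated. On allocation: "we will perform surgeon stratified randomization".

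**The concern.** The section sizes the trial for one test and names another. For two independent groups, the Wilcoxon rank-sum test is the Mann-Whitney test, and the signed-rank test is for paired data. Mann-Whitney is therefore in effect the only test the plan offers for the primary comparison, and no power is given for it. If node counts are normal, as the calculation assumes, Mann-Whitney is slightly less efficient than a comparison of means.

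At stake is how the result is read. A non-significant primary result would be judged against a power figure computed for a different test. Mann-Whitney also does not estimate the mean difference of 6.3 nodes on which the trial was sized, so the test and the target effect are on different scales.

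**Working it through.** **Inputs, all from section 2.7.** Difference 6.3; SD 15; standardised difference 6.3/15 = 0.42; alpha 0.05; power 80%; 89 per group; 10% loss; total 196. Two-sided testing is inferred, because it reproduces 89 (one-sided gives 71).

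**1. Reproduce the stated figure.** For two means, n per group = 2 × (1.960 + 0.842)² × (15/6.3)² = 88.99, so 89. Normal-approximation power at 89 is 80.0%. The plan's figure is exact for the calculation it describes.

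**2. Loss step.** The plan's total is 178 × 1.10 = 195.8, rounded to 196. Losing 10% of 196 leaves 196 × 0.90 = 176.4, about 88 per group. To keep 178 evaluable, 178/0.90 = 197.8, so 198, must be randomised. Moving from 89 to 88 lowers two-means power from 80.0% to 79.6%.

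**3. Power of the named test.** The difference, SD and normal assumption are unchanged. The Mann-Whitney column is simulated with 200,000 replicates (simulation error about 0.1 points).

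| Evaluable per group | Two means, normal approximation | t-test, noncentral t | Mann-Whitney, simulated |
|---|---|---|---|
| 88 (full 10% loss) | 79.6% | 79.1% | 77.0% |
| 89 | 80.0% | 79.6% | 77.8% |
| 95 | – | – | 80.2% |
| 98 (no loss) | 83.7% | 83.3% | 81.6% |

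Two closed-form checks at 88 per group agree:
- Asymptotic relative efficiency: effective n = 88 × 3/π = 84.0, which gives 77.7% in the normal formula.
- Noether's formula: P(X < Y) = Φ(0.42/√2) = 0.617, and Φ(√(6 × 88) × 0.117 − 1.960) = 76.5%.

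For 80% power Mann-Whitney needs 88.99 × π/3 = 93.2 per group by relative efficiency (so 94), 96 by Noether's formula, and about 95 by simulation. With 98 randomised per group, 80% holds only if no more than about 3 per group (3%) lack a node count. At 88 per group, 80% power corresponds to about 6.5 nodes (79.6% simulated).

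**4. Splitting the gap at 88 per group.** From 80.0% to 77.0% is 3.0 points. The t-test itself has 79.1%, so 0.9 points come from the lost patient and the normal approximation, and about 2.1 from the change of test.

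**5. Dependence on distribution.** The documents give no distribution for the count, so these shapes are assumptions (SD 15, difference 6.3, 88 per group, 60,000 replicates).

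| Assumed shape | Mann-Whitney power |
|---|---|
| Uniform | 75.6% |
| Negative binomial, control mean 60 | 79.0% |
| Negative binomial, control mean 50 | 80.3% |
| Negative binomial, control mean 40 | 81.5% |
| Negative binomial, control mean 30 | 84.4% |
| Negative binomial, control mean 25 | 86.7% |

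The unadjusted t-test stays at 79.0% to 79.6% in all of these.

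**6. Scale.** At 88 per group the two-means formula gives 76.9% with SD 15.5. The whole shortfall is about what half a node of error in the SD would cost.

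**The case against.** The strongest reply is that the plan says what its 80% refers to, and on that basis the figure is right. This is a mismatch between sizing method and test; only the loss step is an arithmetic slip. That is fair as a description, but the mismatch remains: the plan gives no power for the test it names.

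The 77% also needs normality and full loss together. Node counts may be right-skewed, where Mann-Whitney does as well as the t-test or better. The count comes from the operation itself, so losses to later follow-up need not remove it. Both points stand, and they limit the finding to the plan's own assumptions. Those assumptions are the only documented ones, however, and the plan itself budgets for 10% loss.

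Stratifying by surgeon can raise the power of even the unadjusted rank test, because balanced surgeon differences still inflate its nominal variance. With 88 per group, normal data and an assumed 11 surgeons, Mann-Whitney power is about 77% if surgeons explain none of the variance and about 78% to 82% if they explain an assumed 10% to 30%. The effect is real, but the documents give neither the number of surgeons nor their variance, and the plan's own 80% ignores stratification too.

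Uncertainty in the SD matters more. Section 2.7 gives no source for the value of 15 (the text there is an unfilled placeholder), and SD 14 or 16 gives 84.7% or 74.3% by the two-means formula at 88 per group. This supports calling the gap modest, but it does not make the stated figure that of the named test.

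Finally, because means and SDs will be reported, the observed mean difference can be read off. That partly meets the point about estimation, although the planned test would not be a test of that difference.

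**Conclusion.** The concern holds. The 80% at 89 per group is correct for a two-sided normal-theory comparison of two means, but it is not the power of the rank test the plan names. With 6.3 nodes, SD 15 and normal data, Mann-Whitney has about 77% power after the full 10% loss and about 82% with none. The change of test accounts for about 2 of the 3 points lost at 88 per group. The loss step accounts for about 0.4 points and two patients.

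The conclusion rests on normality, two-sided testing and no surgeon effect on variance. Right skew or a surgeon effect could bring power back to 80% or above. This is a modest error in the primary sample size statement that should be corrected; it does not put the trial in doubt.

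**What to change.** Either of two changes to section 2.7 joins endpoint, test and sample size.

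- **Keep the rank test and restate the figures.** For example: 196 patients will be randomised, 98 per group. With 10% loss about 88 per group are evaluable, giving about 77% power by Mann-Whitney for a difference of 6.3 nodes (SD 15, normal data), or about 80% for 6.5 nodes. With no loss, power for 6.3 nodes is about 82%.
- **Name as primary the comparison of means that was sized.** A linear model adjusted for the surgeon strata used in randomisation would suit. Unadjusted, power is about 79% at 88 per group. Any gain from adjustment depends on surgeon variance, which the documents do not give, so none should be claimed.

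Under either route, correct the loss step: state that 196 randomised leaves about 88 evaluable per group, or that 89 evaluable per group needs 198 randomised. State that the test is two-sided.

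The cost is wording, plus a simple model under the second route. No added enrolment is required.

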2.2 Background & Rationale, Significance of Selected Topic & Preliminary Data	Administration of muscle relaxation is essential in a variety of procedures as it causes an improvement of surgical conditions. Until recently, intraoperative deep neuromuscular block was eschewed because of concerns about recovery at the end of surgery. Since 2009, many studies have confirmed the rapid efficacy and better safety of sugammadex for reversing moderate and deep neuromuscular blockades induced by steroid muscle relaxants than standard reversing agents, but most of studies have been focused only on surgical condition or concerns from the view points from anesthesiologists.
2.3 Study Design	Prospective, Randomized, double blind controlled trial Multicenter trial : 9 centers

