0	does not respond to pain												
1	does not respond to mild prodding or shaking												
2	responds only after mild prodding or shaking												
3	responds only after name is called loudly and/or repeatedly												
4	lethargic response to name spoken in normal tone												
5	responds readily to name spoken in normal tone												

	
1 Extremely poor conditions: the surgeon is unable to work because of coughing or because of the inability to obtain a visible laparoscopic field because of inadequate muscle relaxation. Additional neuromuscular blocking agents must be given
 
2 Poor conditions: there is a visible laparoscopic field, but the surgeon is severely hampered by inadequate muscle relaxation with continuous muscle contractions, movements, or both with the hazard of tissue damage. Additional neuromuscular blocking agents must be given
 
3 Acceptable conditions: there is a wide visible laparoscopic field but muscle contractions, movements, or both occur regularly causing some interference with the surgeon's work. There is the need for additional neuromuscular blocking agents to prevent deterioration
 
4 Good conditions: there is a wide laparoscopic working field with sporadic muscle contractions, movements, or both. There is no immediate need for additional neuromuscular blocking agents unless there is the fear of deterioration
 
5 Optimal conditions: there is a wide visible laparoscopic working field without any movement or contractions. There is no need for additional neuromuscular blocking agents
 
Ward Pain score using the VAS until postoperative 48 hours PONV Count of rescue medication First flatus time Postoperative complication until POD 30

2.6 Study Duration	2 years after IRB approval

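### Section 2.7 would drop a surgeon at an interim look without a criterion and without protecting patients already randomised, and its primary test ignores the surgeon strata used for randomisation

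*Combined protocol and SAP*

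**What the plan says.** All of the statistical plan is in Section 2.7. On surgeons it makes two statements. The first is that "we will perform surgeon stratified randomization". The second is that for serious "technical problems being able to distort objective data when interim analysis, we would drop the surgeon out of this study". This is the only mention of an interim analysis in the document. Its timing, the decision maker and whether results are seen by arm are not given.

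Quantitative variables, which include the primary endpoint, "were compared by Mann-Whitney and Wilcoxon nonparametric tests". No adjustment for surgeon is mentioned. No intention-to-treat or other analysis population is defined in any section.

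Section 2.1.1 describes the primary endpoint as the "number of harvested lymph node that is critical point regarding quality of surgery". Section 2.3 gives the design as "Prospective, Randomized, double blind controlled trial Multicenter trial : 9 centers". The number of surgeons and their caseloads are not stated.

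**The concern.** Dropping a surgeon has two readings. It can mean that the surgeon enrols no more patients, or that the patients already randomised under that surgeon also leave the analysis. The second removes randomised patients after outcomes have been seen, and nothing in the plan rules it out. What is at stake depends on how the surgeon is chosen. On data pooled over arms, the cost is patients and power. With results by arm in view, the treatment estimate itself can be biased.

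The second issue concerns the same factor. Stratifying by surgeon implies that surgeons are expected to differ in node yield. A test that ignores the strata leaves that variation in the comparison, so it gives up power and runs below its nominal error rate.

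**Working it through.** **The plan's own figure.** Inputs from Section 2.7: difference 6.3 nodes, SD 15, 89 per group, 80% power, and "For all statistical tests, a P value < 0.05 was considered significant". Sidedness is not stated; two-sided reproduces the plan (one-sided would give 71 per group).

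Power = Φ(6.3 / (15 × √(2/n)) − 1.96). With n = 89: 15 × √(2/89) = 2.249; 6.3 / 2.249 = 2.802; Φ(0.842) = 80.0%. The total is 178 × 1.1 = 195.8, or 196. The design reproduces.

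**Assumptions not in the documents.** 9 equal surgeons with 20 patients each (one per centre), total SD 15, ICC for surgeon 0.10, normal data, interim at half accrual, exactly one surgeon dropped. The simulations use the planned Mann-Whitney test.

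**Step 1: choice on pooled data (lowest overall node mean).** Power at a true difference of 6.3:

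| Handling of the dropped surgeon | Patients analysed | Power |
|---|---|---|
| No drop | 180 | 80.1% |
| Discarded | 160 | 75.8% |
| Kept | 170 | 77.7% |
| Kept, others recruit to 180 | 180 | 80.6% |
| Discarded, others recruit to 180 | 180 | 80.7% |

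Bias is nil in every row. Repeat simulations agree to about one percentage point. Replacement needs 180 − 170 = 10 patients if the dropped surgeon's patients are kept, and 180 − 160 = 20 if they are discarded. Over 5, 9 and 18 surgeons and ICC 0.05 to 0.20, discarding without replacement costs 1.3 to 8.7 points and keeping costs 1.2 to 4.7.

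**Step 2: choice informed by arm (ceiling case).** Drop the surgeon with the lowest interim deep-minus-moderate difference; true effect zero.

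| Handling | Bias (nodes) | Deep-favouring error |
|---|---|---|
| No drop | 0 | about 2.0% |
| Discarded | +0.83 | 4.3% |
| Discarded, replaced | +0.74 | not tabulated |
| Kept | about 0 | about 2% |

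The bias is 0.83 / 6.3 = 13% of the target effect. Over the same range of surgeons and ICC it is +0.60 to +0.98. Two-sided error after discarding is about 5% (range 3.5% to 5.8%).

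**Step 3: the cost of keeping.** Take the extreme case in which the 10 retained patients show no effect, using the formula above:

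- Kept: 6.3 × 160/170 = 5.93, 85 per arm, 73.1%.
- Kept with replacement: 6.3 × 170/180 = 5.95, 90 per arm, 75.8%.
- Discarded: 6.3, 80 per arm, 75.7%.
- Discarded with replacement: 6.3, 90 per arm, 80.4%.

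**Step 4: analysing by surgeon.** A linear model with arm and surgeon removes the between-surgeon variance, so the SD becomes 15 × √(1 − ICC). At ICC 0.10 and 90 per arm: 15 × √0.9 × √(2/90) = 2.121; 6.3 / 2.121 = 2.970; Φ(1.010) = 84%. Simulated power with no drop:

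| ICC | 0 | 0.05 | 0.10 | 0.20 |
|---|---|---|---|---|
| Linear model, arm + surgeon | 80% | 82% | 84% | 88% |
| Aligned rank test within surgeon | 78% | 81% | 82% | 87% |
| Planned Mann-Whitney | 78% | 79% | 79% | 81% |

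At ICC 0.10 two-sided error is about 5% for the linear model and about 4% for the planned test.

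**Illustration only.** If node count were the trigger, a 10-patient mean has standard error 15 / √10 = 4.74. The expected lowest of nine standard normals is −1.485, so the lowest of nine equal surgeons would sit on average 4.74 × 1.485 = 7.0 nodes below the overall mean by chance. The documents do not name node count as the trigger.

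**The case against.** The strongest reply is that the rule is conditional, aimed at technique rather than at treatment difference, and sits in a trial described as double blind. On that reading the choice is pooled and there is no bias. This stands, and so do three related points.

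- A reader might infer that retention protects power. It does not. Replacement does, and Section 2.7 does not bar it: "After considering 10% of follow-up loss, a total of 196 patients will be needed". Without replacement, retention gains only about 2 points; with replacement the two options are equal, apart from the 10 extra patients that discarding needs.
- If the weak surgeon's patients truly show no effect, retention costs power: 76% against 80%, both with replacement.
- The simulations drop a surgeon in every run. The loss averaged over the chance that the rule is used at all is smaller and cannot be computed from the documents.

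Stronger readings are not supported. The text does not say that patients will be deleted, that the look is by arm, or that node count is the trigger; bleeding, surgical time and complications are also recorded. Nor does the rule clearly inflate two-sided error under the planned test. Figures of about 6.8% to 7.5% arise in the ceiling case only with a t statistic and no surgeon variance, which is not the planned analysis.

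The objection does not show that the arm-informed route is closed. It also leaves the mismatch between stratified randomisation and unstratified test untouched. That test is not invalid: it has 78% to 81% power and is somewhat conservative.

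**Conclusion.** The point holds as an omission with two parts, and both should be fixed; confidence is medium.

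First, the drop rule has no criterion and leaves randomised patients unprotected. Under a pooled choice the consequence is a loss of about 4 points of power if patients are discarded and not replaced, and no bias. The case for retention rests on the arm-informed choice that the text fails to exclude. There, discarding could add up to about 0.8 nodes and double the deep-favouring error from about 2% to about 4%, with two-sided error near 5%. That is a ceiling, not an expectation.

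Second, ignoring the strata gives up about 5 points of power at ICC 0.10 (about 2 at ICC 0, about 7 at 0.20). This applies whether or not a surgeon is ever dropped.

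All these sizes depend on the assumed number of surgeons, equal caseloads, ICC and normal data.

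**What to change.** **Fix 1.** Replace the drop rule in Section 2.7 with text such as:

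> All randomised patients of every surgeon are included in the primary analysis in the arm to which they were randomised. A surgeon may only be stopped from further enrolment, judged on data pooled over arms against a criterion set in advance. The remaining patients are recruited by the other surgeons. Results without that surgeon are a sensitivity analysis only.

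The criterion, the timing of the look and the decision maker should be written down before any data are seen. If node count is chosen as the measure, the threshold should allow for the chance spread between surgeons; a strict threshold will miss smaller real deficits.

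Cost: one short paragraph and no increase in the planned total. The other surgeons must be able to recruit the missing patients within the study duration of "2 years after IRB approval", and the documents do not describe that capacity. The dilution cost in the extreme case should be accepted openly as the price of keeping the randomised comparison intact.

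**Fix 2.** Analyse the primary endpoint by the randomisation strata: a linear model with arm and surgeon or, if a rank method is preferred, an aligned rank test within surgeon. This needs one sentence and no extra patients. The two fixes belong together: in the ceiling case with patients discarded, the linear model's deep-favouring error would be 5.3% and its two-sided error 6.4%, so adopting fix 2 without fix 1 would leave that route more open.
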